8.3.3 Unanticipated Problems

Unanticipated problems that are also AEs must be reported to the CSO and sent sent by using the REDCap system no later than 7 calendar days of site awareness of the event. UPs that are not AEs are not reported to the Sponsor CSO. Unanticipated problems that are not AEs are not reported to the sponsor CSO. Report unanticipated problems that are also AEs to the CSO according to the sponsor’s reporting guidelines.

8.4 Sponsor’s Reporting Responsibilities

SUSARs, as defined in 21 *Code of Federal Regulations* (CFR) 312.32 and determined by the IND sponsor, must be reported to the FDA and all participating investigators as IND Safety Reports. IND Safety Reports will also be sent to other investigators conducting research under the OCRPRO IND and will be shared with other stakeholders per applicable agreements (e.g. CRADAs and CTAs).

The sponsor will also submit a brief report of the progress of the investigation to the FDA on an annual basis, as defined in 21 CFR 312.33.

AEs that are also unanticipated problems will be summarized by the IND sponsor and distributed to investigators.

8.5 Halting Rules

“Halting” is discontinuation of study agent for all subjects in a study and suspension of enrollment until a decision is made to either resume or permanently discontinue such activity. Subjects are still followed for safety.

8.5.1 Halting Rules for the Study

If the LA Zika vaccine is considered unacceptably reactogenic, as defined below, additional inoculations will be suspended for all subjects and enrollment will be suspended (halted) until the DSMB and study sponsor have reviewed the data and recommend that enrollment and study agent administration can continue. The PI will notify the DSMB at the time that halting criteria are met and obtain a recommendation concerning continuation, modification, or termination of the study. The PI will submit the written DSMB summary reports with recommendations to the IRB(s).

The study PI/protocol chair and/or CSO will determine if the study should be halted. In addition, the FDA may halt the study at any time following review of any safety concerns. A local IRB may halt the study at its site.

8.5.1.1 Halting for Unacceptable Reactogenicity

Following administration of rZIKV/D4Δ30-713, the following criteria will be used to define unacceptable reactogenicity of the rZIKV/D4Δ30-713 vaccine:

1. One or more subjects experience an SAE (as defined in Section 8.1.6 of this protocol) that is determined to be possibly, probably, or definitely related to the administered vaccine (as defined in Section 8.2.4. of this protocol);
2. One or more subjects experience anaphylaxis that is possibly, probably or definitely related to the administered vaccine;
3. One or more subjects experience a Grade 4 adverse event that is definitely, probably, or possibly related to the administered vaccine;
4. Two or more subjects experience the same objective physical finding of severity Grade 3 that is definitely, probably, or possibly related to the administered vaccine, with the exception of Grade 3 erythema at the injection site, as defined in Section 8.2.3. of this protocol;
5. Two or more subjects experience the same Grade 3 laboratory abnormality that is possibly, probably, or definitely related to the administered vaccine;
6. Two or more subjects experience an ANC $\geq 500/\text{mm}^3$ but $< 750/\text{mm}^3$ for > 5 days duration¹;
7. Two or more subjects experience an ANC $< 500/\text{mm}^3$ for any duration¹; or
8. Two or more subjects experience a vaccine-associated Zika-like syndrome, defined as an infection² associated with fever and 2 or more of the following symptoms:
 - a. Grade 2 or greater headache lasting ≥ 12 hours
 - b. Grade 2 or greater photophobia lasting ≥ 12 hours
 - c. Grade 2 or greater generalized myalgia lasting ≥ 12 hours

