rDEN3/4Δ30 [34]	3	20	15	> 10 ⁵ PFU	1.0 ± 0.3	12 ± 0	4.3 ± 0.7
WN/DEN4Δ30 [35]	3	19	16	> 10 ⁴ PFU	0.5 ± 0	15.3 ± 1.9	2.3 ± 0.7

Table 7: Adverse events following one dose of ZIKV/DEN4Δ30 or placebo (CIR 318)

	ZIKV/DEN4Δ30 (n=20)	Placebo (n=8)	P value (1-sided) ¹
Local			
Erythema	5%	0.0%	0.7143

	ZIKV/DEN4Δ30 (n=20)	Placebo (n=8)	P value (1-sided) ¹
Tenderness	0%	0.0%	n/a
Pain	0%	0.0%	n/a
Pruritus	0%	0.0%	n/a
Induration	0%	0.0%	n/a
Systemic			
Fever	0%	0%	n/a
Headache	50.0%	62.5%	0.8454
Rash	0.0%	0.0%	n/a
Neutropenia ²	0.0%	0.0%	n/a
Elevated ALT	0.0%	0.0%	n/a
Myalgia	20.0%	25.0%	0.7922
Arthralgia	10.0%	12.5%	0.8120
Retro-orbital Pain	5.0%	12.5%	0.9259
Fatigue	25.0%	25.0%	0.6940
Muscle weakness	5.0%	0.0%	0.7143
Prolonged PT	0.0%	0.0%	n/a
Prolonged PTT	0.0%	0.0%	n/a
Thrombocytopenia	0.0%	0.0%	n/a

1. P value is the probability is greater for rZIKV/DEN4Δ30 than placebo

2. Neutropenia was defined as an ANC \leq 1,000/mm³.

Table 8: Serological response to a single dose of ZIKV/DEN4Δ30 (n=20)

Geometric mean neutralizing antibody titer (% seroconverted)				# seroconverted (% total)
Day 28	Day 56	Day 90	Peak titer through day 90	
85.6 (41.2, 20%)	66.8 (40.9, 40%)	71.0 (36.6, 45%)	56.1 (40.9, 45%)	(45%)

1. Seroconversion was defined as a titer of ≥ 10 , reciprocal

2. Geometric mean titer calculated at each time point only for those subjects with a titer of ≥ 10 , reciprocal

3. One subject had a titer of >5120 , reciprocal (the ULN). A value of 10,240 was assigned for calculation purposes

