5. Obtain 5 mL of clean-catch urine for virus isolation & culture.
6. Review pregnancy prevention.

Study Day 6 (± 1 day)

1. Screening questions for COVID-19.
2. Perform interim history and focused physical exam, concentrating on any acute complaints.
3. Record vital signs.
4. Obtain approximately 20 mL of blood for CBC with differential, ALT, virology, and PAXGene.
5. Obtain 5 mL of clean-catch urine for virus isolation & culture.
6. Review pregnancy prevention.

Study Day 8 (± 1 day)

1. Screening questions for COVID-19.
2. Perform interim history and focused physical exam, concentrating on any acute complaints.
3. Record vital signs.
4. Nasopharyngeal (NP) or mid-turbinate swab to test for SARS-CoV 2 – the virus that causes COVID-19 – will be collected based on guidance from federal, state, local, and/or institutional health officials* or at the discretion of the clinician (*may be obtained up to 72 hours in advance of study day*).
5. Obtain approximately 50 mL of blood for CBC with differential, virology, and immunology (PBMCs, plasma, and PAXGene).
6. Obtain urine sample for virus isolation and culture.
7. Obtain vaginal secretion sample (women) for virus isolation and culture. Vaginal cup may be inserted at home by the volunteer prior to presentation to the clinic.
8. Obtain semen sample (men) for virus isolation and culture, may be collected at home by the volunteer prior to presentation to the clinic.
9. Obtain oral fluid for serology (CIR subjects only).
10. Review pregnancy prevention.

*This guidance may be informed by the local COVID infection rate, severity of infections, vaccination rates, and other factors as the COVID-19 pandemic continues to evolve and change.

Study Day 10 (± 1 day)

1. Screening questions for COVID-19.
2. Perform interim history and focused physical exam, concentrating on any acute complaints.
3. Record vital signs.
4. Obtain approximately 20 mL of blood for CBC with differential, virology, and PAXGene.
5. Obtain 5 mL of clean-catch urine for virus isolation & culture.
6. Review pregnancy prevention.

Study Day 12 (± 1 day)

1. Screening questions for COVID-19.
2. Perform interim history and focused physical exam, concentrating on any acute complaints.
3. Record vital signs.
4. Obtain approximately 20 mL of blood for CBC with differential, virology, and PAXGene.
5. Obtain urine sample for virus isolation and culture.
6. Obtain oral fluid for serology (CIR subjects only).
7. Review pregnancy prevention.

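### The ANC floor of 500 in halting item 6 means that replacing a prolonged moderate neutropenia with a deeper one of equal length can switch the trigger off

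*Combined protocol and SAP*

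**What the plan says.** Section 8.5.1.1 lists eight criteria for unacceptable reactogenicity. Three can be met by a low absolute neutrophil count (ANC) through a count of subjects:

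- Item 5: "Two or more subjects experience the same Grade 3 laboratory abnormality that is possibly, probably, or definitely related to the administered vaccine".
- Item 6: "Two or more subjects experience an ANC $\geq 500/\text{mm}^3$ but $< 750/\text{mm}^3$ for > 5 days duration".
- Item 7: "Two or more subjects experience an ANC $< 500/\text{mm}^3$ for any duration".

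Table 11 (Section 8.2.3) grades an ANC of 500–749 as Grade 2 and below 500 as Grade 3. Appendix 1 puts exactly 500 in Grade 3 as well, which changes nothing here. Items 6 and 7 require no judgement of relationship to vaccine; item 5 does.

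Other routes exist. Item 1 halts on one related SAE. Item 3 begins "One or more subjects experience a Grade 4 adverse event" and also requires relationship to vaccine. Section 8.5.1 adds "The study PI/protocol chair and/or CSO will determine if the study should be halted", and the FDA or a local IRB may also halt.

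**The concern.** Items 6 and 7 are the plan's numeric neutropenia triggers. A numeric trigger should not become harder to meet when a case gets worse and nothing else changes. Item 6 addresses prolonged neutropenia, and a subject below 500 for 6 days has also been below 750 for 6 days, yet the lower limit removes that subject from the count. Item 7 does not make up for this, because it needs a second subject below 500.

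What follows from meeting a criterion is at stake. Under Sections 8.5.1 and 8.5.2, inoculation and enrollment stop, the DSMB is notified, and the event is reported within 1 business day. If no criterion is met, scheduled DSMB review is twice a year (Section 8.6.3), against a planned enrollment period of 4–8 weeks (Section 4.1.4).

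**Working it through.** The plan states no operating characteristics for the halting rules, so there is no figure of its own to reproduce. The check applies the item wording to cases.

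**Step 1: count subjects under each item.** Take three patterns: M = ANC 600 for 6 days (Grade 2), S = ANC 450 for 6 days (Grade 3), B = a brief dip to 450 (Grade 3). Grade 3 cases are taken as related, which favours item 5. Each item needs a count of 2.

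| Pair | Item 5 | Item 6 | Item 7 | Any met? | Item 6 without floor |
|---|---|---|---|---|---|
| M + M | 0 | 2 | 0 | yes | 2 |
| M + S | 1 | 1 | 1 | **no** | **2** |
| M + B | 1 | 1 | 1 | no | 1 |
| S + S | 2 | 0 | 2 | yes | 2 |
| S + B | 2 | 0 | 2 | yes | 1 |
| B + B | 2 | 0 | 2 | yes | 0 |

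The anomaly is M + S against M + M: same durations, one case deeper, trigger lost. M + B is not claimed to be worse than M + M, because its second case is short. With the floor removed, M + S meets item 6, and every pair that halts now still halts.

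**Step 2: can the patterns be seen?** Under Section 7.4.1, a CBC with differential is drawn on Days 4, 6, 8, 10, 12, 14 and 16 (for Days 10, 12 and 16: "Obtain approximately 20 mL of blood for CBC with differential, virology, and PAXGene"). Four successive nominal draws, such as Days 8 to 14, span 6 days, so a run of more than 5 days can be observed.

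**Step 3: how often would the gap matter?** Inputs: n = 20 vaccinees per cohort (Section 4.1.2). Let a be the chance that a subject is in the 500–749 band for more than 5 days. Let b be the chance of being below 750 for more than 5 days without more than 5 days inside that band, for example by being below 500. Brief dips are set to zero, and all b cases are taken to go below 500 and so count for item 7. Both rates are assumptions.

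- Uncovered pair (exactly one of each): 20 × 19 × a × b × (1 − a − b)^18.
- Halt under items 6 or 7 with the floor deleted (two or more of either kind): 1 − q^20 − 20(a + b)q^19, where q = 1 − a − b.
- Halt under items 6 or 7 now: the second quantity minus the first.

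| a | b | Uncovered pair | Halt now | Halt, floor deleted |
|---|---|---|---|---|
| 1% | 0.5% | 380 × 0.00005 × 0.7618 = 1.45% | 2.13% | 3.57% |
| 1% | 1% | 380 × 0.0001 × 0.6951 = 2.64% | 3.35% | 5.99% |
| 2% | 1% | 380 × 0.0002 × 0.5780 = 4.39% | 7.59% | 11.98% |

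**Step 4: what the data say about rates.** Table 7 (Section 2.3.2) shows no neutropenia in 20 vaccinees at 10³ PFU. Its footnote begins "Neutropenia was defined as an ANC" and sets the limit at 1,000/mm³ or lower. The one-sided 95% upper limit for 0/20 is 1 − 0.05^(1/20) = 13.9%. The event is uncommon, but the data neither show nor exclude the rates above. Cohort 2 receives ten times the dose.

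**The case against.** The strongest objection is that the footnote marked on both items 6 and 7 is not in the supplied copy and may say how duration or cases are counted. That stands as a limit: the finding rests on the item wording, and the footnote must be read before the text is changed.

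Second, a single deep case has its own routes. The note under Appendix 1 assigns Grade 4 to an event judged potentially life-threatening, and Section 8.1.6 includes medically important events among SAEs. A related, prolonged ANC of 450 could be classed either way and would then halt the study alone under item 3 or item 1. It is also more likely to be so classed than a prolonged 600. This narrows the practical gap. However, both routes need a judgement of seriousness or threat to life, and of relationship, and an ANC of 450 triggers neither by itself. They do not restore a trigger that was written to work without judgement.

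Third, the two-subject, same-criterion structure runs through items 4 to 8 and is a design choice. That is a fair reason not to pool a brief dip with a prolonged moderate case. It does not explain why a subject below 750 for more than 5 days should stop counting because the ANC also fell below 500.

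Fourth, the scenario is narrow: one pair of six, and the deeper case must not itself spend more than 5 days at 500–749, or it would count under item 6 as well. The rates are assumed. In a single-dose study, a pair completed after the last inoculation cannot change exposure, so the probability that matters is below the tabulated one. All of this stands and limits the size, not the logic.

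**Conclusion.** The point holds. On the wording of Section 8.5.1.1 and the grades in Table 11, 600 for 6 days plus 450 for 6 days meets none of items 5, 6 and 7, while two subjects at 600 for 6 days meet item 6. This needs no assumed rate. Its likely frequency is low: 1.4% to 4.4% in 20 vaccinees at the rates tried, which are illustrations only. The gap is in the listed ANC triggers and not in safety oversight as a whole. The conclusion is subject to the unseen footnote and is confined to a deep case that is also below 750 for more than 5 days. It should be corrected, because this is a numeric safety rule and the correction is small.

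**What to change.** Delete the lower limit in item 6, so that the criterion is an ANC below 750/mm³ for more than 5 days in two or more subjects, with time below 500 counting toward the duration. Leave item 7 as it is. Check the new wording against the footnote on items 6 and 7. Whether a brief dip below 500 should be pooled with a prolonged moderate case is for the sponsor and DSMB to decide and is not part of this change.

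The cost is one phrase in Section 8.5.1.1 and somewhat more reversible halts. At the three assumed pairs of rates, the absolute rise is 1.4, 2.6 and 4.4 percentage points. In relative terms it is about 68% (3.57/2.13), 79% (5.99/3.35) and 58% (11.98/7.59), which the sponsor should know when agreeing to the change.

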8.5.1.2 Halting for Shedding of Zika vaccine in Semen or Vaginal Secretions

1. Should the Zika vaccine be detected in either semen or vaginal secretions following vaccination, the study enrollment will be halted pending discussion with the DSMB and the FDA. Subjects already enrolled will continue to be followed and additional specimens collected per the protocol.

8.5.2 Reporting a Study Halt

If halting criteria are met, a description of the AE(s) or safety issue(s) must be reported by the PI within 1 business day to the CSO and the local IRB according to their requirements.

- The PI will notify the DSMB
- The CSO or designee will notify all other site Investigators by email or through the specified pathway

8.5.3 Resumption of a Halted Study

The IND sponsor, in collaboration with the PI and DSMB, and in the case of a study halt due to shedding of Zika vaccine in semen or vaginal secretions, with the FDA, will determine if it is safe to resume the study. The CSO or designee will notify the site investigators of the decision to resume the study. The site investigators will notify their local IRB(s) of the decision.

8.6 Safety Oversight

8.6.1 Safety Review and Communications Plan (SRCP)

A Safety Review and Communication Plan (SRCP) has been developed for the protocol. The SRCP is an internal communications document between the PI and the IND sponsor CSO that delineates the safety oversight responsibilities of the PI, the CSO, and other stakeholders. The SRCP also includes the overall plan for conducting periodic safety surveillance assessments.

8.6.2 Sponsor Medical Monitor

A medical monitor, [name], representing the IND sponsor (OCRPRO), has been appointed for safety oversight in this clinical study. The sponsor medical monitor will be responsible for performing safety assessments as outlined in an SRCP, as defined in Section 8.6.1.

8.6.3 NIAID Intramural Data and Safety Monitoring Board

The NIAID intramural DSMB includes independent experts that do not have direct involvement in the conduct of the study and have no significant conflicts of interests as defined by NIAID policy. The NIAID intramural DSMB is constituted to review the safety data of NIAID intramural clinical studies that require DSMB oversight, and consists of experts in infectious diseases, biostatistics, and clinical trials. The PI's designee will provide the DSMB executive secretary with blinding codes in a sealed envelope in case the DSMB requires this information to make its recommendations. The DSMB will review the study prior to initiation and twice a year thereafter. The board may convene additional reviews as necessary. Prior to each review, the PI will submit a summary of cumulative safety data in a format acceptable (by unblinded cohort if requested) to the board. The board will review the study data to evaluate the safety, efficacy, study progress, and conduct of the study. Reports of SAEs will be submitted by the PI to the board at the same time they are reported to the sponsor and IRB. All unanticipated problems will be submitted to the DSMB at the same time they are submitted to the IRB or IND sponsor. IND Safety Reports will be submitted to the DSMB by the investigator after their receipt. The PI will notify the DSMB of any cases of intentional or unintentional unblinding as soon as possible. The PI will notify the board at the time halting criteria are met, and obtain a recommendation concerning continuation, modification, or termination of the study. The PI will submit the written DSMB summary reports with recommendations to the IRB(s).

9 DATA COLLECTION AND MONITORING

9.1 Source Documentation and Data Collection

Complete source documentation (laboratory test reports, hospital or medical records, progress notes, observations, etc.) is required for every study subject for the duration of the study. The subject's study record must record his/her participation in the clinical trial and, after unblinding, the randomization treatment received (with doses and frequency) or other concomitant medications or interventions administered, as well as any adverse reactions experienced during the trial.

Data from source documentation for subjects enrolled in the study will be entered into the Clinical Research Information Management System of NIAID (CRIMSON) Data System. The data entry is to be completed on an ongoing basis during the study. Data entry into CRIMSON will be performed by authorized individuals, and each individual entering data into CRIMSON will have a unique user

ID and password. Corrections to the data system will be tracked electronically (password protected) with time, date, individual making the correction, and what was changed.

Corrections to the source document must be made by striking through the incorrect entry with a single line (taking care not to obliterate or render the original entry illegible) and entering the correct information adjacent to the incorrect entry. Corrections must be initialed and dated by the person making the correction whenever possible. Source documentation should support the data collected in CRIMSON and must be signed and dated by the person recording and/or reviewing the data.

The investigator is responsible for the accuracy, completeness, and timeliness of the data reported to the sponsor in CRIMSON. All data entered into CRIMSON should be reviewed by the investigator/designee, and signed as required with written or electronic signature, as appropriate. Data reported in CRIMSON should be consistent with source documents or the discrepancies should be explained. Source documentation will be made available for review or audit by the sponsor or designee and any applicable federal authorities.

9.2 Study Documentation

Study-related documentation will be completed as required by the IRBs, the sponsor, and regulatory authorities. Continuing review documentation will be submitted by the investigator to the IRBs by the anniversary date of initial review as specified by each IRB. An annual report will be submitted by the sponsor to the FDA according to regulations. These reports will provide a brief description of the progress of the investigation as outlined in 21 CFR 312.33, and will include any protocol revisions if not previously submitted.

The PI will maintain adequate records to account for the disposition of the investigational products, including dates of receipt and quantity, current inventory, and dispensation to subjects. If the study is terminated, suspended, or completed, the PI will return all unused supplies of the investigational product to a NIAID-approved repository or destroy according to the sponsor's recommendation.

9.3 Retention of Specimens

All specimens collected as part of this trial will be stored for future research as part of our approved biosample repository for vaccine research. These samples may be used to learn more about flavivirus infection and other diseases. These samples will not be sold or used to make commercial products. All samples stored in the repository will be labeled with the study subject ID numbers, which, by themselves, cannot identify study subjects, but are linkable to other research databases (e.g., from questionnaires, clinical assessments, logbooks, etc.) generated by the main study. The repository database will contain only the study subject ID numbers. A master log linking the study subject ID numbers to the names of the subjects will be maintained in a password-protected database system with limited access to authorized research team members.

9.4 Retention of Records

The PI is responsible for retaining all essential documents listed in the International Conference on Harmonisation (ICH) Good Clinical Practice (GCP) guidelines. Trial-related documents will

be maintained by the investigator in a secure storage facility for a period of 2 years after final marketing approval of the vaccine or if 2 years have elapsed since the formal discontinuation of the product's clinical development. These records are also to be maintained in compliance with IRB, state, and federal medical records' retention requirements, whichever is longest. The sponsor is required to inform the investigator as to when such documents need no longer be retained. Storage of all trial-related documents will be such that confidentiality will be strictly maintained to the extent provided by federal, state, and local laws.

It is the PI's responsibility to retain copies of source documents until receipt of written notification to the contrary from NIAID OCRPRO. Study documents should not be destroyed without prior written agreement between NIAID OCRPRO and the PI. Should the PI wish to assign the study records to another party and/or move to another location, the PI must provide written notification of such intent to NIAID OCRPRO, with the name of the person who will accept responsibility for the transferred records and/or the new location. NIAID must be notified in writing, and written permission must be received by the site prior to destruction or relocation of research records.

